9.4.2 ANALYSIS OF THE PRIMARY ENDPOINT(S)

9.4.3 ANALYSIS OF THE SECONDARY ENDPOINT(S)

Not applicable

9.4.4 SAFETY ANALYSES

Although we will be unable to determine if there are hospitalizations or ED visits for opioid withdrawal in patients of clinicians in the intervention group, we will monitor this potential safety issue by comparing clinicians who received a letter to controls to determine if there are any dramatic reductions (>20% from baseline) in opioid prescribing in the post-intervention period as a result of the letter. The U.S. does not have an integrated healthcare system with complete data on hospitalizations for all patients to evaluate induced withdrawal. However, it is possible for us to evaluate if providers induce withdrawal on patients by exhibiting high rates of MME reductions (see p. 589 Doctor et al., Science 361, 588–590 (2018)). In our previous work, we demonstrated that for letters, there was no difference in the proportion of prescribers in the intervention or control group who made substantial (>20%) reductions in opioid prescribing in the post-intervention period ($z = 1.279$, $P > 0.05$). We will use this same outcome to evaluate potential harm to patients in this trial.

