4 STUDY DESIGN

4.1 OVERALL DESIGN

This is a decedent-cluster randomized field experiment; clusters of prescribers within each decedent will be randomly allocated to one of two letters interventions. This design avoids treatment contamination—clinicians prescribing to the same patient will be able to share information about the intervention without diluting its effect. If two or more decedents have the same prescriber, that prescriber will be assigned to one and only one of those decedent clusters by random draw. Two factors will serve as random strata: 1) whether the decedent received a prescription from a clinician with a single or multiple deaths, and 2) whether opioids only, opioids in combination with benzodiazepines, or benzodiazepines only were the cause of death. The first strata are designed to form equivalent groups on prescriber risk posture. The second strata equate preference for type of scheduled drug prescribed in practice. Strata will be crossed to form $2 \times 3 = 6$ randomization groups.

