5 STUDY POPULATION

We will intervene on all clinicians and allied health professionals with prescribing privileges and at least one prescription drug death over the course of a year as part of a public health program to encourage safe prescribing in Los Angeles County. Informed consent of patients and clinicians is waived under HHS regulations at 45 CFR 46.116(c), as the study was evaluating a County public service safe prescribing program. As part of the County safe prescribing program, prescribers will be identified in the Controlled Substance Utilization Review and Evaluation System (CURES) system. All California pharmacies and clinics that dispense controlled substances must submit reports to CURES on a weekly basis. In consultation with the program manager of CURES, a letter notifying CURES administrators that prescriptions from these clinicians would be evaluated prospectively after the safe prescribing letters have been sent will be submitted to the CURES system.

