6.3 MEASURES TO MINIMIZE BIAS: RANDOMIZATION AND BLINDING

For randomization, two decedent lists will be generated from the crossed strata levels. Using random.org’s sequence generator, two true random integer sequences derived from atmospheric noise will determine decedent order in each list. For each ordered list, prescribers to decedents in the first half will receive Letter A, the second half of the list will receive Letter B.

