8.2 SAFETY ASSESSMENTS

Although we will be unable to determine if there are hospitalizations or ED visits for opioid withdrawal in patients of clinicians in the intervention group, we will monitor this potential safety issue by comparing clinicians who received a letter to controls to determine if there are any dramatic reductions (>20% from baseline) in opioid prescribing in the post-intervention period as a result of the letter. The U.S. does not have an integrated healthcare system with complete data on hospitalizations for all patients to evaluate induced withdrawal. However, it is possible for us to evaluate if providers induce withdrawal on patients by exhibiting high rates of MME reductions (see p. 589 Doctor et al., *Science* 361, 588–590 (2018)). In our previous work, we demonstrated that for letters, there was no difference in the proportion of prescribers in the intervention or control group who made substantial (>20%)

reductions in opioid prescribing in the post-intervention period ($z = 1.279$, $P > 0.05$). We will use this same outcome to evaluate potential harm to patients in this trial.

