8.3.3.3 EXPECTEDNESS

An AE will be considered unexpected if the nature, severity, or frequency of the event is not consistent with the risk information previously described for the study procedures.

Although we will be unable to determine if there are hospitalizations or ED visits for opioid withdrawal in patients of clinicians in the intervention group, we will monitor this potential safety issue by comparing clinicians who received a letter to controls to determine if there are any dramatic reductions (>20% from baseline) in opioid prescribing in the post-intervention period as a result of the letter. The U.S. does not have an integrated healthcare system with complete data on hospitalizations for all patients to evaluate induced withdrawal. However, it is possible for us to evaluate if providers induce withdrawal in patients by exhibiting high rates of MME reductions (see p. 589 Doctor et al., *Science* 361, 588–590 (2018)). In our previous work, we demonstrated that for letters, there was no difference in the proportion of prescribers in the intervention or control group who made substantial (>20%) reductions in opioid prescribing in the post-intervention period ($z = 1.279$, $P > 0.05$). We will use this same outcome to evaluate potential harm to patients in this trial.

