9.3 POPULATIONS FOR ANALYSES

Intention-to-Treat (ITT) Analysis Population (i.e., all randomized participants)

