9.4 STATISTICAL ANALYSES

9.4.1 GENERAL APPROACH

We will convert opioids to milligram morphine equivalents (MME) using formulas published by the CDC.²⁹ Descriptive and inferential statistics will be carried out in STATA (Version 14.0; Stata Corporation, College Station, TX). The *cmp* command in STATA will be used to compute a difference in differences estimator within a mixed-model censored linear regression.³⁰ The difference in differences estimator compares the average change over time in MME dispensed for prescribers in the group receiving letter version A, compared to the average change over time for those prescribers in receiving version B. To ensure normally distributed data, we evaluate the natural log of MME. Censored regression has a continuous component and a discrete one. The natural log MME doses estimated over days where opioids were dispensed in the name of a prescriber represent the continuous part, and days with no opioids filled in that prescriber's

name represent the discrete part of the model. We denote estimation of the dependent variable as $\log(\widehat{MME})$ * to distinguish it from uncensored estimation. The analysis is represented by:

$$\log(\widehat{MME}) *_{ijk} = \beta_1 x_{1ij} + \beta_2 x_{2ij} + \beta_3 x_{3ij} + \delta_{i(k)} \quad [1]$$

where β_1 , β_2 and β_3 are fixed effects coefficients on time, x_1 , intervention, x_2 , and time by intervention interaction, x_3 , respectively. Alphabetic subscripts describe the i th prescriber, j th prescription filled and k th decedent, the nested random intercept $\delta_{i(k)}$ is normally distributed with mean zero and variance, $\sigma_{i(k)}^2$, for each i prescriber nested in (i.e., having prescribed to) decedent k , $i(k)$. With natural log transformed data, the value $100 \cdot [\exp\{\beta_3\} - 1]$ measures precisely the percentage change in MME attributable to the intervention when data are uncensored (see Woolridge (2008), pp. 212 and 410).

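### The safety analysis compares letter recipients with controls, but every randomized prescriber is assigned a letter, so the comparison cannot be estimated

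*Combined protocol and SAP*

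**What the plan says.** Section 9.4.4 is the whole of the planned safety analysis. It accepts that hospital and emergency visits for withdrawal cannot be observed and substitutes a prescribing proxy: "comparing clinicians who received a letter to controls to determine if there are any dramatic reductions (>20% from baseline) in opioid prescribing". The sentence goes on to treat such reductions as caused by the letter. Section 8.3.3.3 repeats it ("comparing clinicians who received a letter to controls to determine if there are any dramatic reductions"), as does Section 8.2. All three cite an earlier letter-versus-control trial, in which the proportions with reductions above 20% did not differ (z = 1.279), and then carry its outcome over: "We will use this same outcome to evaluate potential harm to patients in this trial".

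The design sections describe something else:

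- Section 4.1: "clusters of prescribers within each decedent will be randomly allocated to one of two letters interventions".
- Section 5: "We will intervene on all clinicians and allied health professionals with prescribing privileges and at least one prescription drug death".
- Section 6.3: "prescribers to decedents in the first half will receive Letter A, the second half of the list will receive Letter B".
- Section 9.3: the population is "Intention-to-Treat (ITT) Analysis Population (i.e., all randomized participants".
- Section 9.4.1: the efficacy contrast sets "prescribers in the group receiving letter version A, compared to the average change over time for those prescribers in receiving version B".

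**The concern.** A comparison with controls needs a group that did not get the letter, and the design does not appear to supply one. Because withdrawal itself cannot be measured, the proxy in Section 9.4.4 carries the whole statistical assessment of patient harm.

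If the text stays as it is, the analyst must choose a comparator after the data are in. The likely choice is Letter A. A null B-versus-A result could then be reported as evidence that letters do not provoke abrupt reductions, which that comparison cannot show.

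**Working it through.** The documents give no sample size, margin or power for the safety analysis, so there is no stated figure to reproduce. The main check is structural.

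**Is there a control group?**

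1. *Arms.* Section 4.1 has two, and both are letters.
2. *Allocation.* Section 6.3 gives half of each decedent list Letter A and the other half Letter B. The halves use up the list: 1/2 + 1/2 = 1, so the share randomized to no letter is 0.
3. *Eligible but untreated.* Section 5 intervenes on all eligible prescribers, so none are held back. Section 4.4 makes having received a letter part of completing the study.
4. *Data source.* Section 8.1 ties each prescriber's data window to the decedent's date of death and the date the letter was sent. No data request for prescribers without a letter is described.
5. *External or historical controls.* None is defined. The only no-letter group in the documents belongs to the earlier trial in Section 2.1 (388 letter, 438 control). The safety sentence was probably adapted from that trial, but this is an inference.

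The letter-versus-control difference therefore has no comparator data.

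**What would B versus A show?**

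Let p0 be the proportion with a reduction above 20% without a letter, s the rise common to both letters, and d the extra rise due to the text added in Letter B. Then

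- A = p0 + s
- B = p0 + s + d
- B − A = d

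The shared rise s cancels. With assumed values p0 = 20%, s = 10 points and d = 0, both arms show 30% and B − A = 0, although the letters raised the proportion by 10 points.

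**Does pre-post change fill the gap?**

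The proportion in each arm with a drop from baseline can be computed, but it mixes the letter with time trends. The data window in Section 8.1 (October 2017 to August 2021) spans the CURES review requirement of October 2, 2018.

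**Illustrative precision of B versus A**

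Inputs from Section 9.2: k = 192 decedents per arm (projected), mean cluster size m = 5.5, CV = 1.22, and ICC 0.05 to 0.20 (not stated for this binary outcome). The base proportion p is not in the documents; 20% to 40% is assumed.

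- n per arm = 192 × 5.5 = 1,056
- Taylor inflation = [1 + (m − 1)·ICC] / [1 − CV²·L·(1 − L)], with L = m·ICC / (m·ICC + 1 − ICC)
- Unweighted inflation = 1 + [(1 + CV²)·m − 1]·ICC
- 95% half-width = 1.96·√(2·p·(1 − p)·inflation / 1,056)

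| ICC | Taylor inflation | Unweighted inflation | Half-width, p = 0.2 | Half-width, p = 0.4 |
|---|---|---|---|---|
| 0.05 | 1.65 | 1.63 | 4.4 points | 5.3 to 5.4 points |
| 0.20 | 2.98 | 3.54 | 5.9 to 6.4 points | 7.2 to 7.9 points |

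The range is about 4.4 to 7.9 percentage points. It indicates what the replacement contrast could deliver; the defect does not depend on it.

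**The case against.** The best defence is that *controls* means Letter A. Section 9.4.1 labels its group term as intervention in a model whose only groups are A and B, and Sections 4.3 and 6.1.1 describe Version B as the letter with extra text. On that reading the safety sentence is loosely adapted wording for B versus A. This is plausible as an account of how the sentence arose, but it does not rescue it. The sentence sets prescribers who received a letter against controls, Letter A prescribers received one, and no section calls Letter A a control. The attribution to the letter would also remain wrong, because B versus A speaks only to the added text.

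A second defence is that safety does not rest on this comparison. The 20% outcome can be computed for each prescriber from the Section 8.1 data, Section 8.3.4 reviews every flagged case, and the efficacy comparison is unaffected. All of that is true, and the repair keeps the case review. But case review estimates no effect. The review load also deserves a check: at the assumed 20% to 40%, 2 × 1,056 prescribers would yield about 422 to 845 flagged cases.

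Two limits on the precision figures also stand. Section 4.1 assigns a shared prescriber to one cluster only, which can lower the mean cluster size. Section 5.1 admits prescribers of any schedule II to IV drug, so some may have no baseline opioid prescribing from which to compute a reduction. Either would widen the intervals. The schema in Section 1.2 could not be seen, but the visible text consistently describes two letters.

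**Conclusion.** The concern holds and must be fixed. The comparison in Sections 8.2, 8.3.3.3 and 9.4.4 cannot be estimated, because 0 prescribers are randomized to no letter and no other comparator is defined. No randomized contrast in this trial can attribute reductions above 20% to receiving a letter rather than none. This conclusion rests on the design text alone.

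The 20%/30% example and the half-widths rest on assumed base proportions, on ICCs not stated for this outcome and on projected numbers of decedents and prescribers. They illustrate the consequence and do not establish it.

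**What to change.** In Sections 8.2, 8.3.3.3 and 9.4.4:

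1. Name the comparison as Letter B versus Letter A in the proportion of prescribers with a reduction of more than 20% from baseline, with a confidence interval that accounts for clustering by decedent.
2. Report the absolute proportion in each arm and overall as description, and keep the case review in Section 8.3.4.
3. Remove the wording that attributes reductions to the letter, and state that harm relative to no letter cannot be concluded from this trial.

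Also correct the description in Section 10.1.6 of a single study arm, which conflicts with the two-arm design.

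If the investigators want a letter-versus-no-letter statement, the plan would have to define an external comparator and its data source. That comparison would not be randomized.

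The cost is wording in four sections and one tabulation on data already requested. Allocation, the efficacy analysis and data collection do not change. The price is a more modest safety conclusion.

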2 INTRODUCTION

2.1 STUDY RATIONALE

One promising strategy for changing physician behavior is through use of “nudges”. The term “nudge” identifies a set of social and cognitive devices that persuade decisions in subtle ways while preserving choice. When prescribing narcotics, physicians may not have recent experiences that come to mind as to why these drugs are dangerous, making risks seem remote. They may also not consult data on a patient’s other narcotic prescriptions in their State’s pharmaceutical drug monitoring program. One useful nudge capitalizes on a finding called “Availability”. Availability is the notion that people rely upon knowledge that is salient, recent and readily available to them to evaluate risks and make decisions. If a physician issued a prescription for a narcotic that resulted in a recent opioid poisoning, providing that physician with this feedback may make the physician more likely to consult a pharmaceutical drug monitoring program database and also prescribe more judiciously.

We published a randomized trial in the journal *Science* demonstrating that carefully crafted letters, supportive in tone and designed to increase the availability of patient harms, are effective in reducing opioid prescribing among high risk prescribers (i.e., those with a death in their practice).⁹ Milligram morphine equivalents in prescriptions filled daily by patients of letter recipients compared to controls decreased by 9.7% (95% confidence interval: 6.2 to 13.2%; $p < 0.001$) over a 3-month period following intervention (Figure 2). We also observed both fewer high dose prescriptions and new patients started on opioids among letter recipients. Learning of a patient's fatal overdose may instill safe opioid prescribing habits in physicians.

Figure 2. Adjusted milligram morphine equivalent prescriptions

Parameter	Randomization group	
	Letter	Control
Prescribers followed	388	438
Preintervention	72.5 (71.3 to 73.7)	71.6 (70.3 to 72.8)
Postintervention	65.7 (63.8 to 67.5)	71.7 (70.0 to 73.5)
Increment (pre- to post-)	-6.8 (-9.9 to -3.8)	0.1 (-2.8 to 3.2)
Difference in increment	-6.9 (-13.1 to -1.0)	
P value	0.001	

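### The safety sections read a non-significant earlier result as no difference in large MME reductions, and carry the outcome forward with no estimate, interval, clustering or existing control group

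*Combined protocol and SAP*

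**What the plan says.** Section 9.4.4 concedes that hospital and emergency visits for withdrawal cannot be observed. It uses a proxy instead: the proportion of prescribers whose opioid prescribing falls by more than 20% from baseline. Essentially the same paragraph stands in 8.2 and 8.3.3.3.

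The paragraph reports that in the earlier letter trial "there was no difference in the proportion of prescribers in the intervention or control group who made substantial (>20%) reductions in opioid prescribing". It says this was demonstrated, and the only support given is z = 1.279 with P above 0.05. It then says: "We will use this same outcome to evaluate potential harm to patients in this trial". None of the three sections gives the two proportions, the direction of the difference, a confidence interval, an analysis model or any statement of how a null result will be read.

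The comparison is described as "comparing clinicians who received a letter to controls to determine if there are any dramatic reductions (>20% from baseline". The design in 4.1, however, is that "clusters of prescribers within each decedent will be randomly allocated to one of two letters interventions", and 6.3 says that "prescribers to decedents in the first half will receive Letter A, the second half of the list will receive Letter B". No group without a letter is described.

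**The concern.** Failing to reject equality is not evidence of equality. A small or noisy data set makes a non-significant result more likely, so it offers least reassurance where it is easiest to obtain. The three sections present such a result as proof that large cuts were no more common in one group. They then adopt the outcome with no other guide to its interpretation.

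This matters because the proportion is the only between-group harm comparison in the plan. If its result is read as the earlier one was, the report could state that no difference was found when the data still allow one of several percentage points. Two further gaps bear on it. Section 9.4.1 handles the nesting of prescribers within decedents for log MME, but nothing extends this to the safety proportion. And the named comparator is not part of the randomised design.

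**Working it through.** **Step 1: the plan's own figure.** Two-sided P = 2 × (1 − Φ(1.279)) = 0.20. This agrees with the stated P above 0.05.

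**Step 2: what that z leaves open in the earlier trial.** The table in 2.1 lists "Prescribers followed" as 388 (letter) and 438 (control). That these were the denominators of the safety test is an assumption. The flagged proportion p is not given, so it is varied.

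SE = √[p(1−p)(1/388 + 1/438)] = √[p(1−p)] × 0.0697. The implied difference is 1.279 × SE, with 95% CI ± 1.96 × SE. In percentage points, signed in the direction of z:

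| p (assumed) | SE | difference | 95% CI |
|---|---|---|---|
| 5% | 1.52 | 1.9 | −1.0 to 4.9 |
| 10% | 2.09 | 2.7 | −1.4 to 6.8 |
| 20% | 2.79 | 3.6 | −1.9 to 9.0 |
| 50% | 3.49 | 4.5 | −2.4 to 11.3 |

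The upper limit is about 5 to 11 points over the whole range. The formula treats prescribers as independent; allowing for clustering would widen the intervals.

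**Step 3: precision in this trial.** Section 9.2 expects 192 decedents per arm and takes a mean of 5.5 prescribers each: 192 × 5.5 = 1,056 per arm. With p assumed at 10-50%, half-width = 1.96 × √[2p(1−p)/1056 × DE], where DE is the design effect.

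The design effect uses the 9.2 inputs: mean size 5.5, CV 1.22, ICC 0.2. That ICC was chosen for the MME sample size; applying it to a binary outcome is an assumption.

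- Independent prescribers, DE = 1: half-width 2.6 points (p = 10%) to 4.3 points (p = 50%).
- DE = 1 + [(1 + 1.22²) × 5.5 − 1] × 0.2 = 1 + 12.686 × 0.2 = 3.54: half-width 4.8 to 8.0 points.

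Two sensitivity checks:

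- A Taylor-type inflation, as 9.2 names that method. λ = (5.5 × 0.2)/(5.5 × 0.2 + 0.8) = 0.579, and DE = 1.9/[1 − 1.22² × 0.579 × 0.421] = 2.98: half-width 4.4 to 7.4 points.
- ICC 0.05, the low end of the usual range quoted in 9.2. DE = 1 + 12.686 × 0.05 = 1.63: half-width 3.3 to 5.5 points.

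**Step 4: the same z here.** If this trial also gave z = 1.279, the upper limit would be (1.279 + 1.96) × SE. That is 4.2 to 7.0 points under independence and 8.0 to 13.3 points with DE = 3.54.

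**Step 5: the comparator.** Section 9.4.4 sets letter recipients against controls; 4.1 and 6.3 send every randomised cluster Letter A or Letter B. The randomisation supports only B against A. If both letters led to the same number of large cuts, that contrast would be zero however many there were.

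**The case against.** The strongest reply is that the plan carries forward an outcome, not a test. A reader might infer a rule under which Letter B is declared harmless whenever P exceeds 0.05. The documents contain no such rule, and the safety text never mentions Letter B. That stands. What remains is that the only worked example of reading this outcome treats non-significance as no difference, and nothing tells the analyst to do otherwise.

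A reader might also infer that letter recipients made more large cuts in the earlier trial. The text gives no direction. If z favoured the letter group, the intervals in step 2 change sign as a harm estimate, and the upper limit for excess cuts falls to about 1 to 2.4 points. The calculation shows only that equality was not demonstrated.

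A third tempting inference is that the safety test will ignore clustering and so have an inflated false-positive rate. The plan names no test for this trial, so no such rate can be attributed to it. The supported statement is that no allowance for clustering is specified.

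Finally, harm can be found in other ways. Section 8.3.4 provides for chart review of every case flagged by the safety measures, with judgments of relatedness and severity, and 10.1.6 names a Safety Officer. None of this depends on a P value, and it would be wrong to say that a non-significant test is the plan's only safeguard. But case review does not compare the groups, so it does not answer the question 9.4.4 poses.

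**Conclusion.** The concern holds in this form. Sections 8.2, 8.3.3.3 and 9.4.4 misread a two-sided P of 0.20 as demonstrated equality. They adopt the outcome as the only between-group harm measure without an estimate, an interval or an allowance for decedent clustering.

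The earlier z leaves open a difference of up to about 5 to 11 points in its own, unstated, direction. This rests on assumed denominators of 388 and 438 and an assumed 5-50% flagged. At the expected size of this trial, the half-width is about 2.6-4.3 points under independence and 4.8-8.0 points with CV 1.22 and ICC 0.2, for an assumed 10-50% flagged. The exact figures move with these assumptions. The conclusion that a non-significant result would not show absence of harm does not.

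The comparator conflict needs no assumption: the controls named in the safety text are absent from the randomised design. Even a tight B versus A interval would show only that the two letters are similar on this outcome.

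**What to change.** Make the same changes in 8.2, 8.3.3.3 and 9.4.4:

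1. Replace the claim of demonstrated equality with the earlier trial's two proportions, their difference and its 95% CI. If these are not to hand, say that no statistically significant difference was found.
2. For this trial, report both proportions and the Letter B minus Letter A difference with a 95% CI that allows for clustering by decedent.
3. State that P > 0.05 will not be read as absence of harm.
4. Reconcile the comparator with 4.1 and 6.3, and state that a B versus A contrast cannot show that either letter is harmless relative to no letter.

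An equivalence margin is not needed for this correction. The documents give none. For an illustrative 5 points and a true difference of zero, the power to exclude it, Φ(5/SE − 1.96) with SE in percentage points, would be only 53% to 23% at DE = 3.54 and 10-50% flagged.

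The cost is a few sentences and one clustered model, with no new data collected in this trial. The safety conclusion becomes more cautious.
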